8.3.7. ACQ-7

The Asthma Control Questionnaire, ACQ-7, is a simple questionnaire to measure the adequacy of asthma control and change in asthma control which occurs either spontaneously or as a result of treatment. The ACQ-7 has 7 items with 1 week clinic recall for items on symptoms and rescue inhaler use. Subjects are asked to recall their experiences during the previous week by responding to 5 symptoms related questions and 1 question related to bronchodilator use and clinic staff complete 1 question on FEV₁%. As part of compliance measure, subjects are required to answer to all of the first 6 questions (eg., symptoms related and bronchodilator use).

It will be used in this study to assess the asthma symptoms (nocturnal waking, symptom on waking, activity limitation, and shortness of breath, wheezing, and short acting β agonist [SABA] usage) and FEV₁ measurement in subjects with active asthma disease.

The items are answered on a 7-point scale (0=totally controlled, 6=severely uncontrolled; and 7 categories for FEV_1 %).

ACQ-7 total score calculated as the mean of the responses to all 7 questions.

ACQ-7 is administered at clinic visits on Day 1, and at Weeks 4, 8, 12 and 16. Baseline ACQ-7 total score is the mean score on Day 1. The ACQ-7 mean score will be calculated for each clinic visit.

Summary statistics for the ACQ-7 score for baseline, each time of measurement, and changes from baseline, will be obtained for each treatment group. A Wilcoxon signed ranks test p-value will be obtained for the within treatment group change from baseline.

The ACQ-7 at Week 16 will be compared between etokimab and placebo groups using an MMRM with change from baseline at Weeks 4, 8, 12, and 16 as response, baseline ACQ-7 total score as a covariate, treatment (3

levels), time (Weeks 4, 8, 12, and 16), and treatment by time interaction as fixed effect factors; and subject as a random effect.

Least squares means for each time of measurement and associated standard errors and 95% confidence intervals will be provided, as well as the p-values for comparing the Week 16 least squares means between each etokimab dose group and the placebo group.

8.3.7.1. ACQ-5

While subjects are expected to respond to all 6 questions (5 symptom related and 1 bronchodilator use items), FEV1 may be still missing if a subject was not able to complete the spirometry test. As a supplementary analysis, the same analyses described in Section 8.3.7 will be repeated on ACQ-5, which is only based on the first 5 symptoms related questions. ACQ-5 total will be calculated in the same way as ACQ-7 and the average of the 5 items will be used for analysis.

8.3.8. Blood Eosinophil Count from Baseline to Week 16

Blood eosinophil count (EOS) is a marker of asthma exacerbation risk, and evidence suggests that reducing EOS leads to improved outcomes in severe asthma. Blood samples for laboratory tests (including eosinophil tests) are collected at each clinic visit.

Summary statistics for eosinophil blood count (absolute) will be provided using n, mean, standard deviation, median, minimum, and maximum at baseline and at Weeks 4, 8, 12, and 16/EOT. Additionally, the within treatment group changes from baseline will be assessed for significance from 0 using a Wilcoxon signed ranks test; the p-value will be presented.

An MMRM will be used to compare each of the etokimab treatment groups with the placebo group with respect to the change from baseline in absolute eosinophil count at Week 16/EOT using the baseline as a covariate, treatment (3 levels), stratification factor, treatment by stratification factor, time (Weeks 4, 8, 12, and 16), and treatment by time interaction as fixed effect factors; and subject (the repeated measures) as random effect. Treatment comparisons between etokimab and Placebo groups will use the Week 16 least squares means and associated standard errors. Ninety-five percent confidence intervals will be obtained for both parameters, and p-values for comparison of etokimab with placebo groups will be presented.

8.3.9. Time to Treatment Discontinuation

Time to treatment discontinuation will be calculated as the number of days from the randomization date to the date the subject discontinued study medication. This variable is censored for subjects who did not discontinue study medication and completed the treatment. The censoring date is the date of treatment completion.

The time to discontinuation will be analyzed using methods for survival data. Kaplan-Meier plots of the estimate of survivor function for the 3 treatment arms will be provided in one graph. A log-rank test will be used to compare each etokimab dose group with the Placebo group.

8.3.10. Incidence of Treatment Discontinuation Due to Oral Corticosteroids or Nasal Polyp Surgery

Use of rescue medication (e.g., systemic corticosteroid) is not permitted in this study (except MFNS as supplied per protocol). If a subject receives systemic rescue treatment, the subject will be discontinued from the study and should return for a final Early Termination Visit (ETV) within 30 days from last dose.

The incidence of treatment discontinuation due to oral corticosteroids or nasal polyp surgery will be summarized in a table showing the number and % of subjects in each group. Comparisons of each etokimab dose group with the Placebo group will be based on a Fisher's exact test.

8.3.11. Change in Nasal Polyp Related Resource Use Questionnaire from Baseline to Week 16

The Nasal Polyp Related Resource Use Questionnaire is a questionnaire of health care resource utilization for nasal polyposis (e.g., specialist visits, emergency care visits, sick leaves, days off) and will be completed as indicated in Table 1.

Outpatient specialist visits will be summarized by visit with number and % of subjects responding. Days missed from work and Days missed from usual activities due to nasal polyp will be summarized with the number of respondents, the mean and standard deviation, median, minimum and maximum.

Change in nasal polyp related resource use from baseline may be evaluated for days missed from work/usual activities due to nasal polyps using the MMRM specified in Section 8.3.8. No formal statistical inference is planned for the rest of the items from this questionnaire.

9. ANALYSIS OF PHARMACOKINETICS

Blood sample for pharmacokinetic analysis will be obtained according to the schedule indicated in Section 9.1. The PK Analysis Set will be used to create subject listings of all concentration-time data following study drug administration and will be presented by subject and actual sample collection time. The PK Analysis Set will be used to list and summarize serum etokimab concentrations for each sampling time point using appropriate descriptive statistics by cohort and nominal study day.

9.1. PK Sampling Schedule

Blood sample for pharmacokinetic analysis will be obtained at each clinic visit according to the schedule in the table below.

Study Day	Study Visit	PK Sample Time Point (Serum)	Sample Time Point for ADA
Day 1/Week 0 etokimab/Placebo dosing	2	Predose	Predose
Day 5/Week 1	3	Must occur 3 to 5 days after Day 1 dosing. PK can be pulled at any time during the study visit	
Day 29/Week4	5	Predose	Predose
	I		
Day 57/Week 8	6	Predose	Predose
Day 85/Week 12	7	Predose	Predose
Day 113/Week 16	8	PK can be pulled at any time during the study visit	Anytime during the study visit
Day 141/Week 20	9	Anytime during the study visit	Anytime during the study visit
Day 169/Week 24/EOS/ET	10	Anytime during the study visit	Anytime during the study visit

Abbreviation: ADA = Anti-drug antibody; EOS = End of study; ETV = Early termination visit and PK=Pharmacokinetic

9.2. Serum PK Endpoints

The PK endpoints for this study will be listed in a separate PK SAP and analysed by AnaptysBio, Inc PK team.

9.3. **Presentation of Concentration Data**

9.3.1. Handling of Missing Data

- Missing PK concentrations will not be imputed, except that if the Day 1 pre-dose concentration is missing then a value of zero will be used.
- If the collection time of a sample is not recorded, then the nominal time will be used to determine PK parameters.

9.3.2. Listing and Presentation of Individual PK Data

- Individual concentration-time data will be listed and plotted by actual sampling times on linear and semi-logarithmic scales.
- Patient listings of PK sampling dates and times and all concentration-time data for each treatment will be presented.
- Graphs for mean concentration-time data following SC administration will be presented by their respective treatment groups. Plots of the mean (±SD) serum concentration-time profile for etokimab by cohort will be presented by nominal sampling time on linear and semi-logarithmic scales.
- Concentration-time data may be summarized by ADA status (confirmed ADA positive versus those without positive ADA response; patients with neutralizing ADAs).

9.3.3. Summary of PK Concentrations

- Mean serum concentrations will be summarized by treatment using descriptive statistics.
- PK concentrations will be summarized by treatment group and nominal time point using n, mean, SD, coefficient of variation (CV), minimum, median, and maximum. For PK concentrations, the number of observations ≥ lower limit of quantitation (LLOQ) will also be included.
- Pharmacokinetic concentration will be reported and analyzed with the same precision as the source data regardless of how many significant figures or decimals the data carry.

10. SAFETY

Safety will be assessed from adverse event (AE) reports, clinical laboratory data, ECG data, physical examination test results, and vital sign parameters. The population used for safety analyses will be the Safety Analysis Set (SS).

All safety analyses will be reported by treatment group as well as combined for the 16-week treatment period unless noted otherwise.

10.1. Extent of Exposure

Etokimab is administered subcutaneously. The predicted etokimab half-life is approximately 14 days. The PK data generated to date indicate that a linear PK profile is observed upon etokimab administration regardless of the route. Hence, for the sake of calculating duration of treatment exposure in this study, we will assume that a subject's exposure to study medication continues up to 28 days after SC injection. Thus, duration of total exposure will be calculated per subject as follows:

Duration of total exposure = (Date of last dose of study medication +28) – Date of first dose of study medication +1

Duration of total exposure and total drug administered will be summarized by treatment group for the Safety Analysis Set using n, mean, standard deviation, minimum, Q_1 , median, Q_3 and maximum. Study drug administration per visit will be listed for the SAF.

10.2. Adverse Events

For the purpose of this study, an adverse event (AE) is any untoward medical occurrence (e.g., sign, symptom, disease, syndrome, intercurrent illness, clinically significant abnormal laboratory finding, injury, or accident) that emerges or worsens following initial administration of the study medication (eg., mometasone furoate nasal spray) and until the end of study participation. The untoward medical occurrence may not necessarily have a causal relationship to the administration of the investigational product. An AE can therefore be any unfavorable and/or unintended sign (including a clinically significant abnormal laboratory result), symptom, or disease temporally associated with the use of a medicinal (investigational) product, whether or not related to the medicinal (investigational) product.

A serious adverse event (SAE) is any untoward medical occurrence that at any dose: results in death, is life-threatening, requires hospitalization or causes prolongation of existing hospitalization.

A treatment-emergent AE (TEAE) is an AE that occurs or worsens in severity after any exposure to the investigational product (etokimab or placebo). If an AE starts between the screening visit and the randomization visit, and is ongoing at the time of treatment initiation, it may be deemed treatment emergent if it worsens in severity/severity. In that case, a separate event is to be recorded in the subject's eCRF indicating the worsened severity.

Section 6.3.4 of this SAP provides conventions for handling missing dates for AEs, for determining treatment emergence in the presence of missing data, and for assigning severity and treatment-relatedness in the presence of partial or missing start/stop AE dates.

All adverse events will be coded using MedDRA version 21.0 or higher. The TEAE reporting period begins with administration of the first dose of study medication on Day 1 and continues until the Visit 7 (Week 16 visit, or 28 days after the last dose of study medication). The Safety Follow-Up AE reporting period begins 29 after the last dose of study medication through completion of the Safety Follow-Up Period (Week 24 visit).

AEs are assessed with respect to relatedness by the investigator, as unrelated, possibly related, related, and definitely related. An AE would be categorized in statistical presentations as "treatment-related" if it is assessed by the investigator as possibly related, related, or definitely related. Any missing relationship will be categorized as "related" for the purpose of summarization.

The severity of AEs (whether nonserious or serious AEs) will be assessed by the investigator as follows:

- Mild: Event may be noticeable to subject; does not influence daily activities; usually does not require intervention.
- **Moderate:** Event may be of sufficient severity to make a subject uncomfortable; performance of daily activities may be influenced; intervention may be needed.
- Severe: Event may cause severe discomfort; usually interferes with daily activities; subject may not be able to continue in the study; treatment or other intervention usually needed.

An AE with missing severity will be categorized as "severe" for purposes of summarization.

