8.6 ADVERSE EVENTS AND SERIOUS ADVERSE EVENTS

8.6.1 DEFINITION OF ADVERSE EVENTS

For this protocol, an AE is any untoward medical occurrence (eg, sign, symptom, disease, syndrome, intercurrent illness, CS abnormal laboratory finding, injury, or accident) that emerges or worsens following administration of the study drug and until the EOS participation. The untoward medical occurrence may not necessarily have a causal relationship to the administration of the IP. An AE can therefore be any unfavorable and/or unintended sign (including a CS abnormal laboratory result), symptom, or disease temporally associated with the use of a medicinal (investigational) product, whether or not related to the medicinal (investigational) product. A treatment-emergent AE is one that occurs after any exposure to treatment.

A pre-existing condition is one that is present prior to the start of the study and is to be reported as part of the subject's medical history. It should be reported as an AE only if the frequency, intensity, or the character of the condition worsens during the study.

Any CS change in the study safety evaluations, (eg, vital signs, physical/neurological examinations, etc.) post injection must be reported as an AE.

For each laboratory test result outside the reference range, the Investigator must ascertain if the abnormal lab result is a CS result for that individual subject. This determination, however, does not necessarily need to be made the first time an abnormal value is observed; the Investigator may repeat

the laboratory test or request additional tests to verify the results of the original laboratory test. If a laboratory value is determined to be a CS result for a subject, this may be considered an AE.

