9.4.3 SAFETY ANALYSES

9.4.3.1 ADVERSE EVENTS AND SERIOUS ADVERSE EVENTS

A TEAE is defined as:

- A new event that occurs during or after first dose of study treatment or,
- Any event present at baseline that worsens in either intensity or frequency after first dose of study treatment.

TEAEs and SAEs will be summarized.

Adverse events will be coded using the Medical Dictionary for Regulatory Activities (MedDRA). The incidence and percentage will be tabulated by preferred term (PT) and system organ class (SOC). An event that occurred 1 or more times on treatment period will contribute 1 observation to the numerator and denominator comprise all safety subjects exposed to etokimab. If the intensity or seriousness of the TEAE changes, the overall intensity or seriousness will be the maximum intensity or seriousness of the multiple occurrences. The TEAEs, SAEs, TEAEs leading to treatment discontinuation, and TEAEs leading to withdrawal of subject will be tabulated for each treatment group. Summaries will also be presented by relatedness to the study drug and the severity of the TEAE.

Listings of AEs, TEAEs, TEAEs leading to death, SAEs, and TEAEs that led to discontinuation from the study or of the study drug will be presented.

Injection site reaction will be reported separately by treatment.

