4.5. Safety Endpoints

Outcome measures are listed below:

- Incidence of adverse events (AEs) and treatment-emergent AEs (TEAEs)
- Incidence of serious adverse events (SAEs)
- Changes in clinical laboratory tests (hematology, chemistry, and urinalysis)
- Changes in vital signs (blood pressure [BP], temperature, respiration rate, and pulse rate [PR])
- Changes in electrocardiogram (ECG) parameters
- Immunogenicity (anti-drug antibody [ADA] and neutralizing ADA)

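### SAP 10.2 drops worsening in frequency from the protocol's TEAE definition, so some events that start before first dose lose their route to TEAE status

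*SAP*

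**What the plan says.** Protocol 9.4.3.1 gives two ways for an event to be treatment-emergent. It is new at or after the first dose, or it meets this test: "Any event present at baseline that worsens in either intensity or frequency after first dose of study treatment".

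SAP 10.2 also has two limbs, but the second is narrower: "A treatment-emergent AE (TEAE) is an AE that occurs or worsens in severity after any exposure to the investigational product (etokimab or placebo". The SAP then adds a rule for an AE that begins between the screening and randomization visits and is still present when treatment starts: "it may be deemed treatment emergent if it worsens in severity/severity". In that case a separate event is to be entered in the subject's "eCRF indicating the worsened severity". Frequency appears in none of these three statements.

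The difference is neither a version effect nor a declared change. SAP Section 2 says the SAP rests on Protocol Amendment 3, which carries the intensity-or-frequency wording. SAP Section 12 lists one departure from the protocol, the handling of nocturnal awakenings. SAP 6.3.4 covers missing dates, severity and relationship, and does not bring frequency back.

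**The concern.** TEAE incidence is a named endpoint. SAP 4.5 lists "Incidence of adverse events (AEs) and treatment-emergent AEs (TEAEs", Protocol Section 3 places it among the secondary endpoints, and the treatment-period adverse-event tables in SAP 10.2.1 count TEAEs. Two definitions give two different sets of subjects with an event. Because the change is undeclared, someone reading the results would assume the protocol's definition had been applied.

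The SAP sentence on ongoing events is also defective in itself. It repeats one word where two different ones must have been meant, and it says only that such an event may be deemed treatment-emergent. A programmer cannot apply it without guessing, and a site following the eCRF instruction has no reason to open a second record when an event becomes more frequent at the same grade.

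**Working it through.** No power or alpha figure is involved, so the check is a comparison of the definitions, case by case.

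| Event | Protocol 9.4.3.1 | SAP 10.2 |
|---|---|---|
| New after first dose | TEAE | TEAE |
| Starts in screening, ongoing at first dose, higher grade afterwards | TEAE | TEAE, through a separate record |
| Starts in screening, ongoing at first dose, more frequent at the same grade | TEAE | No stated route |
| Predates the study, more frequent at the same grade after dosing | TEAE | Depends on how the site records it |

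**Can the severity grade pick up frequency?** Not reliably. The SAP describes a mild event as follows: "Event may be noticeable to subject; does not influence daily activities; usually does not require intervention". The grades turn on discomfort, daily activities and need for intervention. More frequent mild episodes can all stay mild.

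**Why the third row has no other route.** Protocol 8.6.5 has AEs recorded from consent, and the AE definition in SAP 10.2 runs from first use of study medication, with the mometasone spray as its example. An event that starts in the run-in of 20 to 31 days can therefore already be an AE record with a pre-dose start. The SAP calls for a second record only when severity worsens, so a change in frequency alone creates nothing that starts after dosing.

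**Why the fourth row is different.** On conditions present before the study, Protocol 8.6.1 says: "It should be reported as an AE only if the frequency, intensity, or the character of the condition worsens during the study". Such a condition first becomes an AE when it worsens. If the site enters it with a post-dose start date, it can count under the SAP's first limb, as an AE that occurs after exposure. The SAP does not say whether it should.

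**Direction.** Reading intensity and severity as the same scale, every SAP TEAE also satisfies Protocol 9.4.3.1, but not the reverse. The SAP wording therefore leaves each arm's count equal or lower.

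**What one reclassified subject does.** The plan is for about 33 subjects per arm (Protocol 9.2).
- One subject moves a preferred-term row by 1/33 = 3.0 percentage points.
- SAP 10.2.1 tabulates terms reaching 5% in any arm. Since 0.05 × 33 = 1.65, that takes 2 subjects (2/33 = 6.1%). Losing one of two leaves 3.0%, below the cut-off in that arm.
- The overall row counts each subject once, so it moves only if that subject has no other TEAE.

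This shows how coarse the tables are. It does not say how many subjects would be reclassified, and the documents contain no rate from which to derive that.

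**The case against.** The strongest reply is that the SAP's first limb does most of the work. A pre-study condition that becomes more frequent is first reported as an AE after dosing and may enter as an event that occurs. The SAP's general AE definition covers worsening without limiting it to severity. Episodic complaints such as headache may be entered one by one, each with its own start date. The protocol is not uniform either: 8.6.1 has a short definition, "A treatment-emergent AE is one that occurs after any exposure to treatment", which is silent on worsening. Finally, all AEs are listed with TEAEs identified, and worsening asthma is also measured by ACQ-7, ACQ-5 and FEV1.

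Most of this stands, and it confines the point to the third row of the table. It does not dispose of that row. The inconsistency within the protocol is a reason to align all three places.

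Three stronger readings are tempting, and the documents do not support them.
- A reader might infer that every frequency-only worsening drops out of the TEAE endpoint, or that a drug effect on asthma episodes would go unseen. Comorbid asthma is normally pre-study history, so the route through Protocol 8.6.1 is open, and the asthma measures above are analyzed separately.
- A reader might infer that the repeated word in the SAP stands for frequency. The documents do not show which word was lost; Protocol 9.4.3.1 also pairs intensity with seriousness.
- A reader might try to size the loss from the comorbid asthma figure of up to 50% (Protocol 2.1) or the headache figures of 27% to 32% (Protocol 2.3.1). The first is a prevalence of comorbidity and the second is on-study incidence in healthy Phase 1 volunteers. Neither measures AEs that start in the run-in, persist to dosing and then worsen in frequency only.

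**Conclusion.** The protocol and SAP define a TEAE differently and the SAP does not declare it. The clear consequence is limited to AEs that start between screening and first dose, are ongoing at dosing and become more frequent at an unchanged grade. For conditions that predate the study, the outcome depends on site recording practice, which the SAP leaves open.

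The effect runs one way, toward fewer TEAEs. It cannot be sized from the documents. It is probably small, because the affected group must both start an event in a short run-in and worsen in frequency alone. This assumes that sites follow the SAP's eCRF instruction as written and do not open a new record for frequency. If they do open one, the loss shrinks further. The discrepancy should be settled before unblinding, because it decides who counts as having an event in a stated endpoint.

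**What to change.** Make the definitions agree, resting on Protocol 9.4.3.1 and not on a guess at the garbled SAP sentence.

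- In SAP 10.2, define a TEAE as an AE that is new, or that worsens in intensity or frequency, after the first dose of etokimab or placebo.
- Replace the SAP sentence on events ongoing at first dose with the same test, stated as a rule and not as a permission. Require a separate eCRF event for worsening in either respect, with the date of worsening as its start.
- Align the short TEAE definition in Protocol 8.6.1 with 9.4.3.1.

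If the narrower definition is in fact intended, it should be declared and justified in SAP Section 12.

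The cost is a few words in each document and an eCRF completion note. TEAE counts may come out slightly higher. If sites have already been recording under the severity-only instruction, ongoing run-in events may need a query, because a change in frequency may not otherwise be recoverable from the data.

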6.2.3. Study Periods

This study has 3 periods: a 4-week screening period (maximum days 31 days), with a minimum MFNS run-in of 20 days prior to the administration of study medication on Day 1; a 16-week treatment period (Week 0 to Week 16); and an 8-week safety follow-up period.

Period	Start	End
Screening/Baseline	Visit 1 date	Day 1 (Visit 2) date - 1
Treatment Period	Day 1 (Visit 2 date)	Visit 7/EOT date - 1
Safety Follow-up	Visit 7/EOT date	Visit 9/EOS date

Day 1 is Week 0.

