8. EFFICACY

The primary efficacy objective of this study is a comparison of each of two dosing regimens of etokimab with placebo in the treatment of subjects with CRSwNP following a 16-week treatment period (change from baseline using co-primary endpoints). Two co-primary efficacy endpoints will be analyzed.

The analysis of the primary and secondary efficacy parameters will be performed on the FAS, unless otherwise noted. The primary and secondary efficacy analyses will be repeated on the PP analysis set if there are substantial differences between the makeup of the FAS and the PP Analysis Set, in order to assess the impact of major protocol deviations on the key inference.

All primary and secondary efficacy variables will be analyzed for data obtained for the Treatment Period.

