10.2.1. Tabulation of Adverse Event Data

The following tables will be produced to summarize AE data. For the following tables, subjects will be counted only once at each level of summarization.

• An overall summary of the number and percentage of subjects reporting TEAEs, TEAE severity, serious TEAEs, treatment-related TEAEs, related serious TEAs, TEAEs leading to interruption of study drug, TEAEs leading to permanent withdrawal of study drug; related TEAEs leading t

Summary tables by treatment group of the number of subjects (and percentage) with TEAEs as follows:

- TEAEs overall and by system organ class and preferred term
- Most common TEAEs (>=5% in any treatment group) by preferred term
- TEAEs by maximum severity, overall and by system organ class and preferred term
- Treatment-related TEAEs overall and by system organ class and preferred term
- Serious TEAEs, overall and by system organ class and preferred term
- Serious, treatment-related TEAEs overall and by system organ class and preferred term

• TEAEs leading to permanent withdrawal of study medication, overall and by system organ class and preferred term

Additional TEAE summaries will be provided by treatment group, including the number and percentage of subjects experiencing TEAEs for the following:

- TEAEs overall and by SOC and PT, including the following subgroup analyses:
 - Asthma comorbidity

These summaries will be prepared for TEAEs occurring during the treatment period. Similar summaries as above will be provided for AEs starting during the Safety Follow-up Period with the exception of AEs leading to permanent withdrawal of study medication and the subgroup analyses, which will be provided for the TEAEs only. Denominators for the Safety Follow-Up Period AE summaries will be based on the number of subjects entering the Safety Follow-Up Period.

In addition to the listing of all AEs, separate listings will be provided of serious AEs, AEs leading to permanent withdrawal of study medication, and AEs leading to death. TEAEs will be identified on each listing.

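### SAP 10.2 gives two ends for TEAE reporting but one start for follow-up AEs, SAP 6.2.3 draws a third boundary, and nothing says which governs the AE tables

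*SAP*

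**What the plan says.** Four parts of the SAP bear on where the AE tables are cut.

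- **SAP 10.2 (TEAE end).** The reporting period starts with the first dose on Day 1 and "continues until the Visit 7 (Week 16 visit, or 28 days after the last dose of study medication". No rule says whether the earlier or later of these applies, or whether the 28 days are only for subjects without a Visit 7.
- **SAP 10.2 (follow-up start).** "The Safety Follow-Up AE reporting period begins 29 after the last dose of study medication". There is one anchor here, the last dose. The unit is absent from the text as extracted; days is clearly meant, and nothing below turns on it.
- **SAP 6.2.3.** The Treatment Period ends at "Visit 7/EOT date - 1" and Safety Follow-up starts on the Visit 7/EOT date itself.
- **SAP 10.2.1.** "These summaries will be prepared for TEAEs occurring during the treatment period", with a second set for AEs that start in the Safety Follow-up Period. "Denominators for the Safety Follow-Up Period AE summaries will be based on the number of subjects entering the Safety Follow-Up Period". Neither sentence refers to SAP 6.2.3 or to SAP 10.2.

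For context, SAP 10 reports safety by treatment group and "combined for the 16-week treatment period unless noted otherwise". SAP 10.1 uses a 28-day rule for exposure: "we will assume that a subject's exposure to study medication continues up to 28 days after SC injection". SAP 6.3.4 deals only with missing AE dates, severity and relatedness, SAP 12 does not mention the point, and Protocol 9.4.3.1 counts events in the treatment period without giving a cut.

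**The concern.** Incidence of TEAEs is a named secondary endpoint in the protocol synopsis and Protocol 3. The two table sets should divide each subject's time on study once, with no day counted twice and none omitted. The SAP's ends and starts do so only if the same anchor is used on both sides of the boundary, and the SAP does not say to do that.

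The natural reading of SAP 10.2 for a completer is Visit 7 as the end, because the Week 16 visit is named first. Paired with the follow-up start in the next sentence, that reading already breaks whenever Visit 7 is not exactly 28 days after the last injection.

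It matters most for subjects who stop dosing early but stay on study, which Protocol 7.1 encourages and SAP 8.1.1.1 allows. Take one injection on Day 1 and an event on Day 60. By the Visit 7 end the event is a TEAE; by the day-29 start it is a follow-up AE. The number of subjects counted as entering follow-up shifts with the same choice. With no stated rule, whoever programs the tables must pick one, possibly after unblinding.

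Two features of SAP 10.2 add to the difficulty. Its TEAE definition has no end date, so any AE that begins or worsens during follow-up also meets it. It also gives the mometasone spray as an example of study medication, so the phrase last dose should be tied to the injections.

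**Working it through.** **Inputs.** From the schedule of activities (Protocol 1.3, SAP 3.9): fourth injection Day 85 ± 3 (Days 82 to 88) and Visit 7 Day 113 ± 5 (Days 108 to 118). From SAP 10.2: TEAE end at Visit 7 or last dose + 28; follow-up start at last dose + 29. From SAP 6.2.3: treatment end at Visit 7/EOT − 1; follow-up start at Visit 7/EOT.

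Let L be the day of the last injection and V the day of Visit 7.

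**The SAP's implied equivalence.** On target days 85 + 28 = 113, which is Visit 7. SAP 10.2 is then contiguous: TEAEs through Day 113, follow-up from Day 114. SAP 6.2.3 ends treatment at 113 − 1 = Day 112, so Day 113 is TEAE time in one section and follow-up in the other: 1 day.

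**Self-consistent rules.** Ending at L + 28 and starting at L + 29 leaves 0 days in both or neither. So does ending at V − 1 and starting at V.

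**Completers, Visit 7 end with day-29 start (both in SAP 10.2).**
- Days in both = V − (L + 29) + 1 = V − L − 28, when positive. Largest: 118 − 82 − 28 = 8 (Days 111 to 118).
- Days in neither = L + 28 − V, when positive. Largest: 88 + 28 − 108 = 8 (Days 109 to 116).
- Of the 7 × 11 = 77 in-window date pairs, 35 overlap, 35 leave a gap and 7 are contiguous. These counts show the range; they are not probabilities.

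**Completers, sections mixed.**
- SAP 6.2.3 end with SAP 10.2 start: largest gap 88 + 28 − (108 − 1) = 9 days (Days 108 to 116); largest overlap (118 − 1) − (82 + 28) = 7 days.
- SAP 10.2 28-day end with SAP 6.2.3 start: largest gap 118 − (82 + 28) − 1 = 7 days; largest overlap (88 + 28) − 108 + 1 = 9 days.

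**Early stoppers who attend Visit 7 on Day 113, Visit 7 end with day-29 start.** Overlap = 113 − L − 28:
- last dose Day 1: 84 days
- last dose Day 29: 56 days
- last dose Day 57: 28 days

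**The same subjects, 28-day end with SAP 6.2.3 start.** If EOT is taken as Day 113, the gap = 113 − (L + 28) − 1, or 83, 55 or 27 days. If EOT is instead an early visit at the 30-day limit in Protocol 7.1, the gap is (L + 30) − (L + 28) − 1 = 1 day.

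**The case against.** The strongest reply is that each self-contained rule works. SAP 10.2 applied as last dose + 28 and then last dose + 29 divides time cleanly and matches the exposure rule in SAP 10.1. SAP 6.2.3 divides it cleanly too, and SAP 10.2.1 uses its period names. Overlaps and gaps arise only when one rule's end is joined to another's start. That is right. A reader might infer that the SAP specifies a double count or a loss of events; it does not. What remains is that SAP 10.2 itself offers Visit 7 as an end and does not offer it as a follow-up start, so the mismatch is inside one paragraph as well as across sections.

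A reader might also infer that early stoppers lose up to 83 days of AEs from the tables. The documents do not support that as the expected result. It needs the cross-section pairing and an EOT date of Day 113. Protocol 7.1 calls for an early termination visit within 30 days of the last dose, and SAP 6.4 maps EOT and early termination visits by date. The question is not fully closed, because the schedule ties EOT to Week 16 and the early termination visit to Week 24.

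The effect is also small. AE summaries are descriptive, the wording is the same for all arms, and every AE is listed with TEAEs identified. An event in neither table would be absent from the summaries, not from the report. Subjects given systemic rescue leave the study (Protocol 6.5.1), and the planning allowance for dropouts and missing data together is 18%, or 0.18 × 33 ≈ 6 per arm. That is not a count of early stoppers who stay. Finally, the index of tables survives only as a heading in the public text, so a table title naming the period cannot be ruled out.

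**Conclusion.** Wrong as written, minor. SAP 10.2 and 6.2.3 state boundaries that do not agree, and SAP 10.2.1 does not choose between them.

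The discrepancy is 1 day on target days and, within SAP 10.2 alone, up to 8 days for completers at opposite extremes of the visit windows. For early stoppers who reach Visit 7 at Day 113, the overlap is 84, 56 or 28 days under the Visit 7 end and day-29 start. The number of such subjects is not given, so no number of misclassified events can be stated.

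The reach is limited to the descriptive AE summary tables and the follow-up denominator. A reader might infer that the efficacy results are at risk; they are not, because this cut applies to AE tables and efficacy assessments are assigned to visits by the SAP 6.4 windows.

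**What to change.** In SAP 10.2 and 10.2.1, use one anchor for all subjects and all three arms, including early stoppers who stay on study:

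- TEAE tables cover the first etokimab or placebo injection through the last injection + 28 days, or the last visit if earlier.
- Follow-up AE tables start at the last injection + 29 days and run to the last visit.
- The follow-up denominator is the number of subjects still on study on that day.
- Last dose means the last etokimab or placebo injection, not the nasal spray.
- These periods override SAP 6.2.3 for AE tables only.

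The override should go no further, because SAP 8 states "All primary and secondary efficacy variables will be analyzed for data obtained for the Treatment Period". With a fourth injection on Day 82, last injection + 28 is Day 110, and an in-window Visit 7 on Day 118 would fall 118 − 110 = 8 days after it.

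Aligning SAP 10.2 to SAP 6.2.3 would remove the ambiguity equally well. The last-injection anchor is preferred because SAP 10.1 and the follow-up start in SAP 10.2 already use it.

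The cost is a few sentences, with no new data, visits or tables. There is a small downside: for early stoppers, events after last injection + 28 days (such as the Day 60 event above) move to the follow-up tables, and the AE period will differ from the efficacy Treatment Period, so table footnotes should say so.
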